After all patients in all AG019 and Combination cohorts have completed their 6-month follow-up visit unblinding will be done and all data will be analyzed and reported. After completion of the full 12 months follow-up all additional data will be analyzed and reported separately.

More details on the analysis and presentation of study results will be provided in the statistical analysis plan (SAP). The SAP will be finalized prior to the unblinding of treatment allocation codes.

10.1.Study Endpoints

Primary Endpoint

The primary end point will be assessed by analysis of the incidence of treatment-emergent adverse events (TEAEs) collected up to the 6-month follow-up visit. A TEAE is defined as any event not present prior to the initiation of the treatment(s) or any event already present that worsens in either intensity or frequency following exposure to the treatment(s).

Secondary Endpoints

The pharmacodynamic activity of the study drug(s) will be assessed by measurement of biomarkers in blood and serum samples. Relevant parameters will be assessed, including immune markers for effect, relevant T1D parameters and relevant cytokines. Details about the analysis of the collected PD samples will be described in the SAP.

Following parameters will be assessed for analysis of systemic and local exposure to *L. lactis*:

- Presence of live L. lactis clinical strain bacteria in whole blood
- Measurable serum levels of hIL-10 and hPINS
- Presence of *L. lactis* clinical strain bacteria in fecal excretion

Safety information collected at all other time points will be assessed as secondary end points.

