3 EFFICACY AND SAFETY ENDPOINTS

3.1 Primary Endpoint

The primary endpoint will be assessed by analysis of the incidence of treatment-emergent adverse events (TEAEs) collected up to the 6-month follow-up visit. A TEAE is defined as any adverse event (AE) not present prior to the initiation of the treatment(s) or any AE already present that worsens in either intensity or frequency following exposure to the treatment(s).

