3.2 Secondary Endpoints

The PD activity of the study drug(s) is assessed by measurement of biomarkers in blood and serum samples. Relevant parameters are assessed, including immune markers for effect, relevant T1D parameters and relevant cytokines. These will be presented by another CRO and thus will not be a part of the statistical analysis described in this SAP. This SAP will only discuss hemoglobin A1c (HbA1c), insulin use and insulin dose adjusted HbA1c as PD variables as these will be analysed by XXX.

Samples intended for mechanistic assessments are collected from all repeat dose patients in AG019 Cohorts 2 and 4, and from all patients in the combination cohorts. All collected samples intended for mechanistic assessments are planned to be analyzed by a central lab and will not be a part of the statistical analysis in this SAP.

Following parameters are assessed for analysis of systemic and local exposure to *L. lactis* (PK profile):

- Presence of live *L. lactis* clinical strain bacteria in whole blood
- Measurable serum levels of human interleukin 10 (hIL-10) and human proinsulin (hPINS)
- Presence of *L. lactis* clinical strain bacteria in fecal excretion

The PK profile will be presented by Precigen Actobio so PK will not be a part of this SAP.

Safety information collected at all other time points (all Adverse Events (AEs), laboratory variables, vital signs, physical examination, electrocardiogram (ECG), viral status, hypoglycemic events, hyperglycemic events, study drug accountability and concomitant medication) will be assessed as secondary endpoints and analysed by XXX.

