If the start date of an AE is missing, it will be assumed that the AE started after the first administration of IMP. If the start date of an AE is partially missing, and it has started the same year and/or month as the IMP it will be assumed that the AE started after the first administration of IMP. If an AE occurred on the same day as dosing but the onset time is missing the AE will be assumed to be a TEAE.

The infusion of teplizumab was considered withheld if the answer to the CRF question 'Was the Teplizumab infusion given?' was 'No, infusion not started' and/or if the answer on the AE page on 'Action Taken With Study Treatment Teplizumab' was 'Drug interrupted' or 'Drug withdrawn'.

Study treatment of AG019 was considered discontinued if the answer to the CRF question "Action Taken with Study Treatment AG019" was "Drug interrupted" or "Drug withdrawn".

A summary table per cohort will present number of TEAEs, number of unique TEAEs (counted once within each subject at the preferred term level) and number of subjects with at least one event for TEAEs, SAEs, related TEAEs, TEAEs leading to discontinuation of IMP/withdrawal and more.

Tables with

- All AEs by System Organ Class (SOC) and PT,
- All TEAEs by SOC and PT, in total and for the AG019 treatment period only,
- All TEAEs by SOC and PT according to severity, in total and for the AG019 treatment period only,
- All TEAEs by SOC and PT according to relatedness, in total and for the AG019 treatment period only,
- All serious TEAEs by SOC and PT,

will be given. If there are no events an empty table will be produced.

All AEs will be listed. In addition all TEAEs leading to AG019 treatment discontinuation and study infusion withholding will be listed.

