- During treatment: all events reported on the day of treatment start (Day 1) and up to the last treatment day
- Post-treatment: all events reported after the last treatment day

The number of hypoglycemic events and patients with hypoglycemic events will be summarized per cohort, treatment, level and time period.

All hypoglycemic events recorded in the eCRF will be listed. Relative day to treatment start will be included in the listing.

Hyperglycemic events

Major hyperglycemic events will be defined and graded as follows:

- Grade 4 = coma or life-threatening event or event resulting in hospitalization.
- Grade 5 = death.

For this study diabetic ketoacidosis should be reported as grade 4 hyperglycemia (a single adverse event) resulting in hospitalization and/or life threatening consequences.

Hyperglycemic events will be collected and presented as SAEs with no separate tabulation. See section 6.3.9 for further details on presentation.

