6.6 Handling of Dropouts and Missing Data

The data will be analysed as is except for missing dates for concomitant medication and adverse event, see those sections.

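### No TEAE table listed in the SAP applies the primary endpoint's six-month window

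*SAP*

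**What the plan says.** SAP 3.1 sets the primary endpoint as the "incidence of treatment-emergent adverse events (TEAEs) collected up to the 6-month follow-up visit". Protocol 10.1 has the same limit, "collected up to the 6-month follow-up visit". SAP 3.2 then assigns "Safety information collected at all other time points" to the secondary endpoints, so the plan itself draws a primary/secondary line at six months.

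The outputs are described as follows.

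- SAP 6.3.8, tables by SOC and PT: "All TEAEs by SOC and PT, in total and for the AG019 treatment period only". The severity and relatedness tables carry the same two windows.
- SAP 6.3.8, overview: "A summary table per cohort will present number of TEAEs, number of unique TEAEs", plus numbers of subjects with events. No window is given. The serious-TEAE table has none either.
- SAP 7.1, section 14.3: the only window in any TEAE table title is the AG019 treatment period.

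On timing, SAP 6.9 places the primary analysis after all patients have passed Day 180 and, where possible, reuses the tables planned for the final output. Protocol 5.10 and the opening of protocol 10 say that all data are analysed and reported once the 6-month visits are complete, and that further data after 12 months are reported separately. Protocol 10.8 restricts the data to six months only for the Phase 1b preliminary analysis. Its item on the analysis that contains the primary endpoint does not repeat the restriction.

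**The concern.** A programmer who follows SAP 6.3.8 and 7.1 as written produces no table of the primary endpoint. For repeat-dose and combination patients, one stated window is too short (56 days) and the other is open-ended. The open-ended one mixes events that SAP 3.2 calls secondary into what readers will take as the primary result. Because cohorts were enrolled in sequence, a single calendar cut gives them different lengths of follow-up. Columns set side by side in a TEAE table would then not cover the same time at risk. In a descriptive study these tables are the result, so the window belongs in the plan.

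**Working it through.** **1. Windows side by side (repeat-dose and combination patients)**

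| Item | Window | Share of 180 days |
|---|---|---|
| Primary endpoint (SAP 3.1, protocol 10.1) | first IMP to Day 180 visit | 100% |
| AG019-period tables (SAP 6.3.8, 7.1) | 56 days | 56/180 = 31% |
| In-total tables, final output | to study exit, about Day 360 | 360/180 = 200% |
| Overview, serious, discontinuation tables | none stated | not defined |

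The TEAE definition in SAP 6.3.8 has a start but no end, and protocol 8 collects AEs to study exit. Neither supplies the missing limit. Single-dose patients are followed for 4 days and are not affected.

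**2. Who could be past Day 180 at the primary cut**

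SAP 6.9 says that two interim analyses have been performed. Assume that the second followed the protocol 10.8 milestone and that nobody withdrew.

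- Phase 1b repeat-dose: 4 cohorts × 6 = 24 (minimum 4 × 4 = 16).
- Combination Cohort 1: 12.
- Combination Cohort 2, open-label: 2.
- Total: 24 + 12 + 2 = 38 of 48 (79%), or 16 + 12 + 2 = 30 of 40 (75%) without re-enrolment.

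This counts patients with follow-up beyond the endpoint window. It does not count patients with events there.

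**3. Possible effect on the reported figure**

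The documents give no incidence, no late event rate and no enrolment dates, so what follows is illustration. Let p be the six-month incidence, g the extra days of follow-up after Day 180, and r the event rate after Day 180 relative to before.

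- Incidence shown in total = 1 − (1 − p)^(1 + r·g/180).
- Relative rise in the number of events = r·g/180.

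| g, r (assumed) | p = 10% | p = 20% | p = 30% | p = 90% | Event count |
|---|---|---|---|---|---|
| 11 days, 0.25 | 10.1% | 20.3% | 30.4% | 90.3% | +1.5% |
| 90 days, 0.5 | 12.3% | 24.3% | 36.0% | 94.4% | +25% |
| 90 days, 1 | 14.6% | 28.4% | 41.4% | 96.8% | +50% |
| 180 days, 1 | 19.0% | 36.0% | 51.0% | 99.0% | +100% |

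The 11 days are the shortest possible lead of the second open-label patient over patients 3–12 in Combination Cohort 2 (Day 12 minus Day 1, with no review time). The 180 days are Day 360 minus Day 180. The 90-day rows are intermediate choices.

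In patients, a move from 20% to 36% is 6 × 0.16 = 0.96 of 6 in an AG019 cohort. In a combination active arm (2 open-label + 8 randomised = 10) it is 10 × 0.16 = 1.6.

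**4. Which visit is Day 180**

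The SAP counts 19 visits: screening is Visit 1, Days 1–12 are Visits 2–13, and Days 28, 56, 90, 180, 270 and 360 are Visits 14–19. Visit 17 is therefore Day 180. The ECG taken only on suspicion of cardiac problems falls at Visit 17 in SAP 6.3.9 and at Day 180 in protocol 7.3.4.2, which agrees.

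**The case against.** The best defence is that the window is already fixed in SAP 3.1, that SAP 6.9 names the Day 180 analysis as the primary one, and that protocol 5.10 and 10 keep the six-month report apart from later data. On this view a table list need not repeat the endpoint definition, and the endpoint wording could even mean a study-level data cut.

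Part of this stands: the plan clearly intends a six-month primary report. But separate reporting does not remove post-Day-180 events already collected from patients enrolled earlier, and protocol 10 says that all data are analysed at that point. The per-patient reading is the natural one, because the limit is a patient's visit. The SAP also does state windows for its tables, and they differ from the endpoint's. This is therefore more than a detail left unsaid. The table shells, the Pre-Analysis Review Form and the Interim Analysis Plan were not available and might hold the cut.

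Three stronger readings are tempting, and the documents do not support them.

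- A reader might take SAP 6.6, "The data will be analysed as is except for missing dates for concomitant medication and adverse event", as a decision not to truncate. That section concerns missing data and is silent on the event window.
- A reader might infer the same from the hypoglycaemia periods, such as "Post-treatment: all events reported after the last treatment day". Those serve a secondary output and say nothing about the primary endpoint.
- A reader might conclude that the randomised comparison is distorted or that events are hidden. Within a combination cohort the randomised comparison is largely unaffected, and a longer window adds events without concealing any.

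**Conclusion.** The mismatch is real and can be checked line by line: the primary endpoint has a six-month window, and no listed TEAE table uses it. The count of 38 of 48 (or 30 of 40) rests on the second interim having followed protocol 10.8 and on no withdrawals.

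The numerical effect cannot be known from the documents. The range of 20.3% to 36.0% for a 20% six-month incidence rests wholly on assumed late hazards and follow-up. Its upper end needs an undiminished event rate for 180 further days, although AG019 stops at Day 56 and teplizumab at Day 12.

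The practical consequence is limited. The study is descriptive with no tests (SAP 6.4, 6.5), and SAP 6.3.3 puts the relative day in the listings, so the six-month figure can be rebuilt. This is a gap between endpoint and tables that should be closed. It is not a loss of data or a threat to the study's validity.

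**What to change.** In SAP 6.3.8 and 7.1, add or relabel two outputs for repeat-dose and combination patients as the primary endpoint: the per-cohort TEAE overview and the TEAE table by SOC and PT. Restrict both to onset from first IMP through each patient's Day 180 visit (Visit 17). Use relative day 180 if that visit is missed, and last contact if the patient withdraws earlier. Apply the same cut at the third interim and in the final analysis. Keep the in-total and AG019-period tables as secondary.

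Settle this before the blind is broken for the third interim, which is when SAP 6.9 already requires decisions on blinded subjects' data to be complete. If the shells or the Pre-Analysis Review Form already hold this cut, a sentence in the SAP stating it is enough.

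The cost is SAP wording, one date filter and a few repeated tables, with no new data and no change to trial conduct.

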6.3.9 Other Safety Assessments

Vital Signs

For repeat dose patients, weight, sitting blood pressure, heart rate, respiratory rate and body temperature will be measured at Visit 1, 2, 5, 8, 13-19. Height is measured at Visit 1. For single dose patients vital signs will be measured at screening, treatment and post treatment.

For all vital signs parameters summary statistics will be produced for observed values. In addition, the difference from baseline to each visit at which they were assessed will be derived and presented.

Shift tables showing the number of subjects who changed from normal, abnormal not clinical significant or abnormal clinical significant at baseline to normal, abnormal not clinical significant or abnormal clinical significant at each post-baseline time of assessment will be presented.

All vital signs will be listed.

Clinical Laboratory Measurements

From screening to the last visit lab parameters will be collected, see CSP Appendix A for details.

Parameters to be analysed will include:

- Hematology: complete blood count: Red Blood Cell (RBC) count, haemoglobin, haematocrit, mean corpuscular volume (MCV), mean corpuscular haemoglobin (MCH), mean corpuscular haemoglobin concentration (MCHC), RBC distribution width (RDW), white blood cell (WBC) count, differential count, platelet count
- Serum Chemistry: blood glucose, sodium, potassium, chloride, calcium, CO₂/bicarbonate
- Liver function tests: alkaline phosphatase (ALP), Aspartate Aminotransferase (AST), Alanine Aminotransferase (ALT), lactate dehydrogenase (LDH), total protein, albumin, total bilirubin
- Pregnancy tests for women of childbearing potential: serum (at screening), urine (at other visits)
- Coagulation tests: international normalized ratio (INR)
- Inflammatory: C-reactive protein (CRP)

Following additional blood parameters will be analysed at screening, and if no concerns are identified, these parameters will not require analysis at follow-up visits:

- Kidney function tests: uric acid, urea/blood urea nitrogen (BUN), creatinine, estimated glomerular filtration rate (eGFR)
- Cardiovascular tests: total cholesterol, triglycerides, high density lipoproteins (HDL), low density lipoproteins (LDL), very low density lipoproteins (VLDL - optional)
- Thyroid stimulating hormone (TSH)

In addition to the above lab assessments to be analysed by the site's local lab, EBV/CMV/HCV/HBV/HIV monitoring assessments will be done. These measurements were performed at screening for all patients and at Visit 13-16, Visit 19 for repeat dose patients. Potential reactivation will be assessed at regular intervals by polymerase chain reaction (PCR) for viral load.

For hematology, clinical chemistry, liver function, coagulation parameters and CRP summary statistics will be produced for observed values. In addition, the difference from baseline to each visit at which they were assessed will be derived and presented.

Shift tables showing the number of subjects who changed from normal, abnormal not clinical significant or abnormal clinical significant at baseline to normal, abnormal not clinical significant or abnormal clinical significant at each post-baseline time of assessment will be presented.

Figures showing mean and median values over time per cohort will be shown for CRP, AST and lymphocytes.

Number of patients with positive/negative serology at baseline and positive/negative for PCR per visit will be tabulated.

All laboratory parameters will be listed. Abnormal values will be flagged in listings.

In addition, all study patients (except for the single dose patients) will receive a XXX continuous glucose monitor (CGM) device for the entire duration of their study participation. The data generated by the device will be downloaded at every site visit. The devices will store data for up to 30 days. The device measures glucose every 5 minutes, thus every measurement will be said to have a duration of 5 minutes when the calculation of total duration is performed. The first measurement is said to measure the glucose value 5 minutes before the actual measurement. For the CGM data collected at each visit:

- The total CGM recording time,
- Time in range (the time greater than or equal to 71 mg/dl and less than or equal to 179 mg/dl),
- Time above range (the time above 179 mg/dl),
- Time in the low range (the time below 71 mg/dl),
- Time in the very low range (the time below 50 mg/dl) and
- Time with missing values

will be summarized in hours/minutes and percentages of the total CGM recording time, per cohort.

Physical Examination

The physical examination included visual inspection of skin, examination of eyes, ears and throat, auscultation of heart, lungs and abdomen, and percussion/palpation of abdomen. The results will be recorded as

- Normal,
- Abnormal Not Clinically Significant or
- Abnormal Clinically Significant.

For repeat dose patients the physical examination will be performed at Visit 1, 2, 5, 8, 13-19. For single dose patients the physical examination will be performed at screening, treatment and post treatment.

The frequencies (and percentage) of normal, abnormal but not clinically significant or abnormal and clinically significant will be tabulated.

Physical Examination data will be listed.

ECG

The investigator will perform a 12-lead ECG. The results will be recorded as

- Normal,
- Abnormal Not Clinically Significant or
- Abnormal Clinically Significant.

For single dose patients ECG status will be collected at screening (Visit 1) and at post treatment only if there is a suspicion of cardiac problems. For repeat dose patients ECG status will be collected at Visit 1, Visit 15, Visit 19 and in addition at Visit 17 if there is a suspicion of cardiac problems.

The frequencies (and percentage) of normal, abnormal but not clinically significant or abnormal and clinically significant will be tabulated.

ECG data will be listed.

Hypoglycemic events

Hypoglycemic events will be documented in the patient diary. Events of hypoglycemia will be classified as outlined below.

- hypoglycemia Level 1: A glucose alert value of 3.9 mmol/l (70 mg/dl) or less for at least 20 minutes
- hypoglycemia Level 2: A glucose level of <3.0 mmol/l (<54 mg/dl), sufficiently low to indicate serious, clinically important hypoglycemia.
- hypoglycemia Level 3: Severe hypoglycemia, as defined by the American Diabetes Association, denoting severe cognitive impairment requiring external assistance for recovery.

For the purposes of this study, hypoglycemia events classified as level 1 will not be recorded separately on the hypoglycemia event electronic case report form (eCRF), unless the investigator feels that the event is medically important. Hypoglycemia events level 2 and 3 will be recorded separately on the hypoglycemia event eCRF. The evaluation that produced the value or result should be repeated until that value or result returns to normal or can be explained and the participant's safety is not at risk. In addition, all hypoglycemia events meeting the definition of SAE should be recorded as serious adverse events in the eCRF.

Time of the events will be divided in the following time periods:

- Pre-treatment: all events until the day before treatment start
- During treatment: all events reported on the day of treatment start (Day 1) and up to the last treatment day
- Post-treatment: all events reported after the last treatment day

The number of hypoglycemic events and patients with hypoglycemic events will be summarized per cohort, treatment, level and time period.

All hypoglycemic events recorded in the eCRF will be listed. Relative day to treatment start will be included in the listing.

Hyperglycemic events

Major hyperglycemic events will be defined and graded as follows:

- Grade 4 = coma or life-threatening event or event resulting in hospitalization.
- Grade 5 = death.

For this study diabetic ketoacidosis should be reported as grade 4 hyperglycemia (a single adverse event) resulting in hospitalization and/or life threatening consequences.

Hyperglycemic events will be collected and presented as SAEs with no separate tabulation. See section 6.3.9 for further details on presentation.

